Study Protocol

Project title:

Determination of DNA repair products in urine after UV irradiation of the skin

Sponsor and principal investigator

[name] Pharm, PhD

Bispebjerg Hospital, University of Copenhagen

Department of Dermatology, D92

[name]

[name]

Direct: [name]

Cell: [name]

Mail: [contact]

Participants:

[name] (EE), PhD

Bispebjerg Hospital, University of Copenhagen

Department of Dermatology, D92

[name]

[name]

Mail: [contact]

[name] [name], [name] et [name]

Bispebjerg Hospital, University of Copenhagen

Department of Dermatology, D42

[name]

[name]

Mail: [contact]

Anthropologist [name]

Bispebjerg Hospital, University of Copenhagen

Department of Dermatology, D92

[name]

[name]

Mail: [contact]

1. Titel

Determination of DNA repair products in urine after UV irradiation of the skin.

2. Purpose

Problem definition

DNA damage is formed in the skin by sun exposure ¹. The most common DNA damage is called thymine dimers (Figure 1). Many of these injuries are repaired by "Nucleotide excision repair" (NER) and excreted through the urine ². The importance of this repair mechanism is seen in patients with defects in their NER, who have a very high risk of developing skin cancer. We want to be able to quantify the amount of thymine dimers in the urine after ultraviolet (UV) irradiation of the skin. With the establishment of such a test system, it will eventually be possible to test potential photoprotective substances or potential photocarcinogenic substances based on damage measured in the urine after a known UV dose. We would like to investigate when the highest secretion of this type of DNA damage occurs using 6 different irradiation regimens. It has previously been possible to quantify thymine dimers in the urine using an isotope method, but that method is no longer available and it is desirable to avoid isotopes ³. We have developed a new method based on mass spectrometry (UHPLC-MS).

UVR-induced DNA damage and repair

[figure not shown]

Figure 1. DNA damage of the thymine dimer type occurs by UV irradiation of the skin. The damage will often be repaired and excreted in the urine.

Hypothesis

Our hypothesis is that maximum excretion of thymine dimers in the urine occurs 1-4 days after UV irradiation of the skin.

Endpoints and rationales

The primary endpoint is quantification of thymine dimers in the urine before irradiation as well as every day for up to 7 days after UVR irradiation with six different irradiation regimens in healthy subjects. The 2-3 days where the concentration of excreted thymine dimers is greatest will be the days to collect urine in future studies. One of the six irradiation regimens will consist of healthy volunteers going sun holiday outside of Denmark. The volunteers will receive a UV-dosimeter which measures the UV dose at their location. The urine collection will follow the same procedure as the other groups, upon returning to Denmark.

The secondary endpoints are changes in redness and pigment, measured non-invasively using surface reflectance measurement.

The 6 irradiation regimens will be compared so that the greatest amount of thymine dimers can be determined with the least change in pigment and redness.

Background

Ultraviolet (UV) radiation causes DNA damage in the skin that can eventually lead to skin cancer ¹.

Thymine dimer is a DNA damage that is only formed when UV rays hit DNA in the skin cells ¹.

Nucleotide excision repair (NER) repairs and removes thymine dimers in the individual cell, which are then excreted in the urine ². Thymine dimers in the urine are a biomarker for the total DNA repair³. In the past, a method for quantifying thymine dimers in urine using isotope labeling³ has existed. The method was very sensitive but had a long analysis time and in addition it is an advantage from a work environment to avoid working with radioactive isotopes³.

We have succeeded in developing a new method of analysis using Ultra High-pressure Liquid Chromatography Mass Spectrometry (UHPLC-MS). This method has high sensitivity and high selectivity while having a fast analysis time. In addition, this equipment is capable of analyzing multiple DNA modifications. Furthermore, there is high sensitivity and high selectivity. This study is a proof-of-concept study in which we would like to investigate when the most optimal time for urine collection is after six different irradiation regimens. The perspective is to be able to use the method to find new potential photo-protective as well as photocarcinogenic substances.

3. Method

Study design for healthy subjects

The subjects will be recruited by a notice on Bispebjerg's hospital website and by anthropologist [name].

For five of the six irradiation regimens the subjects will be divided into 2 groups of 8-10 people (group 1-5). Group 1 is irradiated 3 times with 1 standard erythema dose (SED). 1 SED corresponds to approx. 10 min sun around kl. 13 on a good Danish summer day. Group 2-5 will be irradiated once with up to 3 SED, which corresponds to approx. 30 min around kl. 13 on a good Danish summer day. Group 6 consists of subjects going on sun holiday.

Subjects in group 1-5 are irradiated in a full body UV cabin (Waldmann, Willing-Schwenningen, Germany) with 26 F85 / 100W UV6 tubes (290-350 nm, broad spectrum), TL-01 (290-380 nm, Philips, Eindhoven, The Netherlands) or TL-12 (280-380, Philips, Eindhoven, The Netherlands). Dosages are

measured out by multiplying the CIE erythema spectrum with the UV-spectra to achieve the same biological effect in the skin. The irradiation time is set on a timer clock, so that the UV cabin switches off after the desired irradiation time. The irradiation time is 13 seconds for 1 SED and 39 seconds for 3 SED. The UV cabin is measured using calibrated equipment, which is also used to measure our UV cabins in the clinic, which are used for patients. The subjects stand up in the cabin and have a screen on so that their eyes and face are not exposed to radiation. When lighting, subjects should only wear underwear, which for men are underpants / boxer shorts, while for women it is bras and panties.

The following groups will be irradiated:

Group 1: 3x1SED in underwear corresponding to approx. 80% irradiated body surface area

Group 2: 1x3SED in underwear corresponding to approx. 80% irradiated body surface area

Group 3: 3x3SED in underwear corresponding to approx. 80% irradiated body surface area

Group 4: 3x3SED wearing shorts and bra/naked torso corresponding to approx. 60% irradiated body surface area

Group 5: 3x3SED wearing shorts and T-shirt corresponding to approx. 40% irradiated body surface area

Group 6: up to 30 subjects who are already planning a sun vacation. The individuals should behave in the sun as they normally do and not do anything differently. The subjects will be provided with a dosimeter, which measures the UV dose at their location. The test subjects will also receive a form where they have to note their clothing/sunscreen consumption. The subjects will be asked 4 questions before they go on vacation (appendix 1) and must undergo a qualitative interview (appendix 2) when they return from vacation and receive their urine test results.

The experiment is performed between October and March in Denmark, to avoid that the subjects do not simultaneously receive UV radiation from the sun and thus can form DNA damage. Subjects must collect morning urine in dispensed containers and must store it in their own freezer until the final visit.

Morning urine samples (2x 50 ml) will be collected before irradiation, labeled as day 1 and up to day 10 for groups 1, 3, 4, and 5, and day 8 for group 2. Group 6 will collect a urine sample in Denmark before the vacation starts and then collect urine as the other 5 groups do when they are back in Denmark. A total of 1000 ml of urine (2 x 50 ml x 10) will be collected for groups 1, 3, 4, 5, and 6, and 800 ml of urine (2 x 50 ml x 8) will be collected for group 2. Before and after each illumination are

measured pigment and redness on the subjects as well as on final visits. Pigment and redness measurement are performed on the back, chest and buttocks.

4. Statistical considerations

Previous studies have observed an increase of 1.7 nmol with a standard deviation (SD) of 1.3 nmol ⁴, with a power of 0.80, as well as significance level of 0.05 in a paired test, then 7 persons must complete the study when we set power to 0.80 and have a significance level of 0.05 and uses the paired test (Power and Sample Size Calculation, PS, Vanderbilt University; version 3.1.2). As the study lasts up to 10 days, dropouts can be expected and therefore 8-10 subjects are included in each of the groups 1-5, as well as up to 30 subjects in group 6. There is an expectation of a larger variability in group 6 due to the varying doses the subjects will receive during their vacation.

5. Subjects

A total up to 80 subjects are recruited to participate in the study. Men and women aged 18 or over who meet the criteria for inclusion and exclusion will be included. The subjects are recruited through Bispebjerg Hospital's intranet and by anthropologist [name]. Subjects will be invited to an initial screening visit where they will receive oral information about the study by trial supervisor [name], [name] or [name]. The meeting takes place in a separate room to ensure a safe and quiet environment. Subjects will be informed that they can bring an assistant if they wish. Written informed consent will be ensured, and takes place at least 24 hours after the screening visit.

Inclusion criteria

Over the age of 18

Written informed consent from the subject.

Exclusion criteria

Immunosuppressed individuals

Sun holiday / ski holiday / solarium 4 weeks before trial start

Skin disease

Medicines that cause photosensitivity or affect DNA repair

Pregnancy

6. Risks, side effects and disadvantages in the short and long term

There is a slight risk of short-term redness after irradiation, as well as after staying in the sun. The UV doses (3 SED) have been chosen so that almost all Danes will avoid redness. The total UV dose corresponds to a ½ hour stay in the sun in the middle of the day during the summer in Denmark. All subjects will be informed both orally and in writing about the risks and possible side effects.

Extraction of new biological material or collection of biological material from already existing biobank

No biobank. The urine samples are analyzed immediately after collection. Excess biological material is destroyed immediately after analysis.

7. Quality control

The Helsinki II Declaration will be respected as well as the standards of good clinical research. Respect for privacy as well as for physical and mental integrity in patients is maintained. The study will be registered at the Knowledge Center for Data Reporting, the Capital Region, in the electronic system Pactius.

8. Data protection and storage

The general data protection regulation will be respected. Research using data from the capital region is considered public research. Use and distribution of data collected in this study will be discussed with patients during the consent process. The project is reported to the Knowledge Center for Data Reporting, the Capital Region of Denmark in the electronic system Pactius. A list of the subjects' names, study ID and date of birth is prepared. All collected data will be anonymised and protected by Danish legislation regarding the handling of personal data and the Health Act. Data are registered and stored for 5 years after completion of the study at the Department of Dermatology, Bispebjerg Hospital.

9. Economy

It is Pharmacist [name], [name] [name] and Engineer [name] who have taken the initiative for the experiment and they are all paid by the department of dermatology, Bispebjerg hospital. There is no contribution from companies to this experiment. An external grant of 500,000 DKK has been received from the Danish Research Center For Skin Cancer (<https://vhk.org/en>), which is intended to cover the salary for [name] as well as chemicals for urine analysis. [name] has a grant from the Lundbeck Foundation, which covers a taxable compensation of 750-1,500 DKK per participant as inconvenience compensation.

750 DKK will be paid if the exposure is completed and 4 urine samples are provided for groups 1-6. 1,000 DKK will be paid if the exposure is completed and all urine samples are provided for groups 1-5. For group 6, 1,500 DKK will be paid if all urine samples are provided, and both the vacation and interview are completed.

10. Information for subjects

The principle investigator, [name], is responsible for providing clear oral and written information about goals, designs and risks of the study, as stated in "Information and consent to participate in health science research projects" by the Ministry of Health and the Elderly. In undisturbed surroundings, the participant will be made aware of their right to have one / or more attendants present, that participation is voluntary and that withdrawal is possible at any time during the study. Subjects are given sufficient reflection time (at least 24 hours). Subjects will be asked to sign a consent form.

11. Publication of results

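### Groups 3-5 are listed for 3x3SED (9 SED, about 90 minutes of sun), but Section 3 prose says one irradiation and Section 6 gives a half-hour total, a third of their dose

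*Combined protocol and SAP*

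**What the plan says.** Section 3 (Method, Study design for healthy subjects) describes the lamp regimens twice. The opening prose says group 1 has three irradiations of 1 SED and then states "Group 2-5 will be irradiated once with up to 3 SED", which it equates to about 30 minutes of midday summer sun. The group list further down has "Group 2: 1x3SED in underwear corresponding to approx. 80% irradiated body surface area" but "Group 3: 3x3SED in underwear corresponding to approx. 80% irradiated body surface area". It gives groups 4 and 5 the same 3x3SED over about 60% and 40% of body surface. On lamp time, "The irradiation time is 13 seconds for 1 SED and 39 seconds for 3 SED".

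Later in Section 3, the morning urine samples are "labeled as day 1 and up to day 10 for groups 1, 3, 4, and 5, and day 8 for group 2", and "800 ml of urine (2 x 50 ml x 8) will be collected for group 2", against 1000 ml for the other groups.

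Section 6 (Risks, side effects and disadvantages) names 3 SED as a dose chosen so that nearly all Danes will not redden. It then says "The total UV dose corresponds to a ½ hour stay in the sun" at midday in the Danish summer. It makes no exception for any group.

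**The concern.** The two descriptions in Section 3 cannot both be true of groups 3-5. A ceiling of 3 SED might be read as a per-session limit, but the prose also fixes the number of sessions at one.

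The more serious consequence is in Section 6. UV is the hazard this study imposes deliberately, and Section 2 says that it causes DNA damage that can lead to skin cancer. Section 6 is meant to cover long-term as well as short-term risk, so the cumulative dose is a figure it has to get right. If the list is correct, someone weighing the lamp risk from Section 6 would assess 3 SED when three of the five lamp groups receive three times that. The protocol also promises subjects oral and written information on risks. That information is not in the documents, but if it repeats the half-hour figure, those subjects would be told too low a total.

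**Working it through.** **Inputs, all from the protocol.** 1 SED is about 10 minutes of midday sun (Section 3 prose). Lamp time is 13 s per SED (39 s for 3 SED; 39/13 = 3). Sessions and dose per session come from the group list. There are 8-10 subjects in each of groups 1-5.

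**Formulas.** Cumulative dose = sessions x SED per session. Sun equivalent = SED x 10 min. Lamp time = SED x 13 s.

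**Reproducing the stated total.** Half an hour is 30/10 = 3 SED. The totals by group are:

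| Group | Sessions x SED | Total SED | Sun equivalent | Lamp time | Ratio to 3 SED |
|---|---|---|---|---|---|
| 1 | 3 x 1 | 3 | 30 min | 39 s | 1 |
| 2 | 1 x 3 | 3 | 30 min | 39 s | 1 |
| 3, 4, 5 | 3 x 3 | 9 | 90 min | 117 s | 3 |

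The half-hour figure reproduces for groups 1 and 2 and fails for groups 3, 4 and 5.

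**Which description is intended?** Two things point to the list.

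- *Urine schedule.* Groups 3-5 are sampled to day 10 (2 x 50 ml x 10 = 1000 ml), like group 1, which has three sessions. Group 2, with one session, stops at day 8 (2 x 50 ml x 8 = 800 ml). Section 2 sets collection at "every day for up to 7 days after UVR irradiation with six different irradiation regimens in healthy subjects", and the pre-irradiation sample is day 1. One session on day 1 plus 7 days ends on day 8. If three sessions fall on days 1-3, then 3 + 7 ends on day 10. The irradiation days are not stated, so the consecutive-day pattern is an assumption, but the two extra sampling days match two extra sessions.
- *Distinct regimens.* If the prose were right and the full 3 SED were given, groups 2 and 3 would be the same: one 3 SED exposure in underwear over about 80% of body surface. There would then not be six different regimens.

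**How many subjects.** Groups 3-5 hold 3 x 8 to 3 x 10 = 24-30 of the 5 x 8 to 5 x 10 = 40-50 lamp subjects, or 60%.

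**Does the smaller exposed area offset the dose?** SED x body-surface fraction is 9 x 0.8 = 7.2 in group 3, 9 x 0.6 = 5.4 in group 4 and 9 x 0.4 = 3.6 in group 5, against 3 x 0.8 = 2.4 in groups 1 and 2. It does not, even in group 5. The protocol's sun-time equivalent is not area-weighted, so this is only a side check.

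**The case against.** The strongest reply is that this is a drafting slip whose answer lies in the same section. The regimens are set out group by group and the urine schedule agrees with them, so staff are unlikely to give the wrong number of sessions. That is fair, and the point does not rest on mis-dosing.

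For Section 6, one can argue that the redness sentence refers to the dose per session and is therefore not contradicted. That stands. The same reading might be tried on the next sentence, but it speaks of a total, and 3 SED is not the total for groups 3-5.

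Four further objections limit the scope:

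- The participant information has not been seen, so any harm through consent is conditional.
- The session interval can largely be inferred from the sampling days. Asking for it is a request for clarity and not part of the error.
- The area-weighted figures are not a protocol measure, and the conclusion does not need them.
- Group 6 has an uncontrolled holiday dose, so 9 SED is the maximum for the lamp groups only. The half-hour total does not describe group 6 either.

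These narrow the point but leave it in place: a cumulative exposure in the risk section is wrong on the protocol's own figures.

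**Conclusion.** The concern holds. Two sentences are wrong for groups 3-5: the Section 3 prose on the number of irradiations, and the Section 6 total. The second matters more. It gives 3 SED (about 30 minutes) where these groups receive 9 SED (about 90 minutes), low by a factor of 3 for 60% of the lamp-irradiated subjects.

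This rests on the group list being the intended regimen, which the sampling schedule and the distinctness of groups 2 and 3 support strongly and which the sponsor can confirm. It needs no outside source. It does not say that 9 SED is unsafe, only that the stated total is not the dose planned.

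**What to change.** In Section 3, change the prose so that group 2 is irradiated once with 3 SED and groups 3-5 three times with 3 SED each, after the sponsor confirms the list. In Section 6, replace the single total with cumulative doses by lamp group: 3 SED (about 30 minutes of sun) for groups 1 and 2, and 9 SED (about 90 minutes) for groups 3-5. Base the lamp risk statement on 9 SED, and say that group 6 receives a variable holiday dose outside these totals. Check that the participant information carries the same figures.

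While the text is open, it would help to state the interval between sessions and whether the redness reassurance is per session or also covers three 3 SED sessions.

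The cost is a protocol amendment, plus new participant wording only if it contains the half-hour figure. The stated exposure becomes less favourable for groups 3-5. Design, endpoint and sample size do not change.

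### Redness and pigment are read only at sites that group 5's T-shirt and shorts cover, so the skin-change comparison between regimens favours group 5

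*Combined protocol and SAP*

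**What the plan says.** Under Endpoints and rationales (section 2), changes in redness and pigment, read by surface reflectance, are the secondary endpoints. The six regimens are to be compared so that the "greatest amount of thymine dimers can be determined with the least change in pigment and redness".

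Section 3 says where the readings are taken: "Pigment and redness measurement are performed on the back, chest and buttocks". No other site is named and no group is exempted. Readings fall before and after each illumination and at the final visit.

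The group list in section 3 defines the last cabin regimen as "Group 5: 3x3SED wearing shorts and T-shirt corresponding to approx. 40% irradiated body surface area". Groups 1 to 3 wear underwear (about 80% exposed). Group 4 wears shorts with a bra or bare torso (about 60%).

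Two other sentences in section 3 conflict with that list. One covers clothing in general: "When lighting, subjects should only wear underwear". The other covers dose: "Group 2-5 will be irradiated once with up to 3 SED", whereas the list gives 3x3 SED for groups 3 to 5.

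**The concern.** A T-shirt covers the back and chest, and shorts cover the buttocks. In group 5 the device therefore reads only skin that was not irradiated, while the arms and legs that were irradiated are never read. In groups 1 to 4 the back is at least largely exposed. The same endpoint thus measures irradiated skin in four groups and covered skin in the fifth.

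Skin change is one of the two criteria on which the regimens are compared. For group 5 that criterion will be close to zero whatever its exposed skin does. A reader of the results could conclude that the group 5 regimen is gentle on the skin when the data cannot show this either way.

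**Working it through.** The plan gives no sample size, test or expected size for redness or pigment, so there is no figure of its own to reproduce on this point. Its one sample-size figure, 7 completers, concerns the urine endpoint and plays no part here.

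**Inputs.** Number of exposures, SED per exposure, clothing and exposed area come from the group list in section 3. Measurement sites and times come from section 3, and group sizes of 8-10 from section 4.

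**Assumption.** Clothing blocks UV. Fabric transmission is not given, but the drop from 80% to 60% to 40% across groups 3 to 5 shows that the protocol itself counts clothed skin as not irradiated.

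**Step 1: dose by site, as listed.** Cumulative dose on exposed skin = exposures x SED per exposure. Dose at a site is that value if uncovered and about 0 if covered.

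| Group | Exposed skin (SED) | Back (SED) | Buttocks (SED) |
|---|---|---|---|
| 1 | 3 x 1 = 3 | 3 | 0 |
| 2 | 1 x 3 = 3 | 3 | 0 |
| 3 | 3 x 3 = 9 | 9 | 0 |
| 4 | 3 x 3 = 9 | 9 | 0 |
| 5 | 3 x 3 = 9 | 0 | 0 |

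The chest follows the back, except where a bra covers it. The buttocks are covered in all five groups, so only the back and chest can separate the regimens, and both are covered in group 5.

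**Step 2: two contrasts.**
- Groups 4 and 5 have the same listed dose on exposed skin (9 SED) and differ only in clothing, but the back receives 9 against 0 SED. A difference between them at the back reflects site placement, not how irradiated skin reacted.
- Groups 1 and 2 give exposed skin 3 SED against 9 in group 5 (9/3 = 3 times), yet the back receives 3 SED in those groups and about 0 in group 5.

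**Step 3: both criteria together.** As a rough stand-in for dimer yield (an assumption; the documents give no such model), take cumulative SED x exposed fraction:
- Groups 1 and 2: 3 x 0.80 = 2.4
- Group 3: 9 x 0.80 = 7.2
- Group 4: 9 x 0.60 = 5.4
- Group 5: 9 x 0.40 = 3.6

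As measured, group 5 would beat groups 1 and 2 on dimers (3.6 v 2.4) and on skin change (0 v 3 SED at the back). It stays below groups 3 and 4 on dimers.

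**Step 4: the single-exposure sentence.** If it applies to groups 2-5, exposed skin in group 5 receives at most 3 SED, the same maximum as group 2, and the back still receives about 0 against up to 3. The proxy becomes 3 x 0.40 = 1.2 for group 5 against 2.4 for group 2, so the apparent win on both criteria disappears. The bias in the skin readings does not.

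**The case against.** The underwear-only sentence, if it governed, would expose group 5's back and remove the problem. It cannot govern without leaving the 60% and 40% figures with no basis and making groups 3 to 5 one regimen. The documents do leave the contradiction open, and the finding rests on the group list.

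The contrast is also narrower than three sites. The buttocks are covered in every cabin group and may be meant as a reference, though the protocol does not say so. In women a bra may cover part of the chest and back in groups 1 to 4, and the exact measuring spot is not given. This stands, but it leaves the back as the main informative site, and group 5 has no reading of irradiated back skin.

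Dose at a site is not itself a change in redness or pigment. Section 6 states: "The UV doses (3 SED) have been chosen so that almost all Danes will avoid redness". The bias in redness may therefore be small, and could show more in pigment or after repeated exposures. That too stands: the direction is clear, but the size on the endpoint's own scale cannot be derived from the documents.

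Finally, this is a secondary endpoint in a proof-of-concept study, with no rule for weighing skin change against dimers. No wrong choice of regimen follows automatically, and the claim that group 5 beats groups 1 and 2 on both criteria depends on the 3x3 SED listing and the proxy. These points limit the consequence without removing the bias.

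**Conclusion.** The concern holds. On the group list, none of the three measured sites is irradiated in group 5 (8-10 subjects), and the least-change criterion favours that group because of where the readings are taken. The discrepancy is about 0 SED at the measured sites against 9 SED on exposed skin, or against at most 3 SED if the single-exposure sentence applies. The conclusion assumes that clothing blocks UV and that the clothing in the group list is what subjects wear. The primary urine endpoint is untouched. This should be fixed because the comparison as written would mislead and the remedy is cheap.

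**What to change.** - **Site.** Add a reflectance site that is uncovered in all of groups 1-5, such as the forearm or lower leg, or substitute it for one current site. Base the redness and pigment comparison between regimens on that site, as change from each subject's own baseline.
- **Control.** State that the buttocks are the covered control site.
- **Subjects already measured.** Where the new site is missing, do not interpret group 5's back and chest readings as the response of irradiated skin, and leave them out of the least-change comparison.
- **Group 6.** Clothing on holiday varies, so a fixed site may or may not have been exposed. Say how these readings enter the six-regimen comparison; the clothing form already planned can support this.
- **Text.** Reconcile the underwear-only sentence with the clothing in groups 4 and 5, and the single-exposure sentence with the 3x3 SED listing.

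**Cost.** As listed, an added site needs 3 x 2 + 1 = 7 readings per subject in groups 1, 3, 4 and 5, and 1 x 2 + 1 = 3 in group 2. That is 4 x (8 to 10) x 7 = 224-280, plus (8 to 10) x 3 = 24-30, giving 248-310 readings over 40-50 subjects with the same device at the same visits. A swap adds none. Two downsides remain: subjects already measured lack the new site, and limb skin may respond differently from trunk skin, so groups should be compared only at the same site.

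### The 0.80 power in Section 4 covers only a within-group rise over baseline; the promised regimen comparison has no allocation rule or defined contrast, and the regimens themselves are described inconsistently

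*Combined protocol and SAP*

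**What the plan says.** Section 4 takes an increase of 1.7 nmol with SD 1.3 nmol from earlier work, a significance level of 0.05 and a paired test, and concludes "then 7 persons must complete the study when we set power to 0.80". To allow for dropout, it plans 8-10 subjects in each of groups 1-5 and up to 30 in group 6. It contains no other calculation and no analysis method.

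The stated aims are wider:

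- **Timing (Section 2, Hypothesis):** "Our hypothesis is that maximum excretion of thymine dimers in the urine occurs 1-4 days after UV irradiation of the skin".
- **Endpoint (Section 2, Endpoints and rationales):** thymine dimers before irradiation "as well as every day for up to 7 days after UVR irradiation with six different irradiation regimens".
- **Regimens (same section):** the six regimens "will be compared so that the greatest amount of thymine dimers can be determined with the least change in pigment and redness".

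On allocation, Section 3 says only that "the subjects will be divided into 2 groups of 8-10 people (group 1-5"). Group 6 consists of people who have already planned a sun holiday.

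On the regimens, Section 3 first says "Group 2-5 will be irradiated once with up to 3 SED". Its list then gives "Group 3: 3x3SED in underwear corresponding to approx. 80% irradiated body surface area", and also gives groups 4 and 5 as 3x3SED with smaller exposed areas. Section 6 equates the total UV dose with half an hour of midday summer sun.

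**The concern.** The regimen comparison is a between-group question, and its result is meant to inform later studies. Three things it needs are missing or unsettled.

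1. **Allocation.** No rule says who enters which of groups 1-5. If groups fill by order of arrival, convenience or preference, differences between subjects (in pigment, for example) could be read as regimen effects.
2. **Contrast and precision.** No per-subject summary, model or expected precision is given. A reader could take 0.80 as the power of the whole study. A non-significant difference between two small groups could then be misread as showing that the regimens are equally good.
3. **What is being compared.** On one of the two descriptions, group 3 is the same regimen as group 2.

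The paired test also does not match the hypothesis. Showing that excretion rose above baseline does not show on which day it was highest.

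**Working it through.** **1. The plan's own figure.** Inputs from Section 4: increase 1.7 nmol, SD 1.3 nmol, alpha 0.05. Assumed: two-sided test, and 1.3 is the SD of the within-person change. Power comes from the noncentral t with df = n - 1 and noncentrality (1.7/1.3) x sqrt(n).

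| Completers | 6 | 7 | 8 | 10 |
|---|---|---|---|---|
| Power | 0.727 | 0.820 | 0.885 | 0.956 |

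Seven is the smallest number that reaches 0.80, so the figure reproduces. A one-sided test would need only 6 (0.862). If 1.3 were the SD at a single time point, the SD of change would be 1.3 x sqrt(2(1 - r)). Power at n = 7 would then be 0.54, 0.66, 0.82 and 0.98 for assumed before/after correlations r of 0, 0.25, 0.5 and 0.75.

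**2. Precision for a pair of regimens.** Assumed: SD of change 1.3 nmol in every group, variance pooled over five groups (df = 5n - 5), two-sided 0.05, no multiplicity adjustment. The standard error of a difference is SD x sqrt(2/n).

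| | n = 7 | n = 10 |
|---|---|---|
| Standard error (nmol) | 1.3 x sqrt(2/7) = 0.695 | 1.3 x sqrt(2/10) = 0.581 |
| 95% CI half-width (nmol) | 2.042 x 0.695 = 1.42 | 2.014 x 0.581 = 1.17 |
| Difference detectable with 80% power (nmol) | 2.01 | 1.66 |
| The same, SD 1.0 to 1.6 | 1.55 to 2.48 | 1.28 to 2.05 |

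The SD for cabin irradiation is not in the documents, hence the range. Averaging over days or adjusting for baseline would reduce these values somewhat.

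**3. Regimen descriptions side by side.** Section 3 equates 1 SED with about 10 minutes of sun.

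- Three SED once: 3 x 10 = 30 minutes, which agrees with Section 6.
- 3x3 SED: 9 x 10 = 90 minutes, which does not.

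Dose times exposed area (SED x body fraction) for groups 1 to 5:

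- On the group list: 3 x 0.8 = 2.4; 3 x 0.8 = 2.4; 9 x 0.8 = 7.2; 9 x 0.6 = 5.4; 9 x 0.4 = 3.6.
- If groups 2-5 are irradiated once with 3 SED: 2.4; 2.4; 2.4; 1.8; 1.2. Group 3 then equals group 2.

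**4. Collection days.** The pre-irradiation sample is labelled day 1. Collection ends on day 8 in group 2 and day 10 in groups 1, 3, 4 and 5. With seven days of follow-up, 8 - 7 = 1 and 10 - 7 = 3. This fits a last irradiation on day 1 in group 2 and on day 3 in the others. It is an inference, because the spacing of irradiations is not stated.

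**The case against.** The strongest reply is that this is a proof-of-concept study, that the hypothesis concerns timing, and that the regimen comparison is not itself a named endpoint. Section 2 does say what is to be weighed: dimers against redness and pigment. Baseline urine and pigment are measured, the study runs from October to March, and recent sun exposure is an exclusion, all of which limit or reveal imbalance. This supports calling the comparison exploratory. It does not supply an allocation rule or settle what the regimens are, and the plan does not itself call the comparison descriptive.

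Several stronger readings are tempting but unsupported:

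- **That the sample size is wrong.** It is arithmetically right for its test, on the two assumptions named above.
- **That the different end days are an error.** They are consistent with equal follow-up after the last irradiation. Samples need only be aligned by time since irradiation.
- **That regimens are confounded with lamp type.** Section 3 names three lamp types without tying them to groups, but "The irradiation time is 13 seconds for 1 SED and 39 seconds for 3 SED" gives one time per dose, which suggests a single setting. This needs clarification only.
- **That the comparison is hopeless.** Bonferroni over ten pairs would lower the power for a 1.7 nmol difference to 0.23-0.42, but the plan promises no such tests. Equality of all five regimens is also implausible on the group list. If excretion were proportional to dose times area, a single trend across groups 1-5 would have power 0.49-0.65 (n = 7-10) if 1.7 nmol belongs to group 3, and above 0.99 if it belongs to groups 1-2.

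**Conclusion.** The point holds in this limited form. The 0.80 is sound for a within-group rise over baseline, provided that the test is two-sided and 1.3 nmol is the SD of change. It covers neither the day of maximum excretion nor the regimen comparison. For a pair of regimens, the difference detectable with 80% power is about 2.0 nmol (7 completers) to 1.7 nmol (10), at an assumed SD of 1.3 nmol and without multiplicity adjustment. Large dose contrasts may be seen; neighbouring regimens may not be separated. The size of any allocation bias cannot be computed from the documents.

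The contradiction between a single irradiation and 3x3SED for groups 3-5, together with the half-hour total, is an error in the text whatever analysis is chosen. The documents do not settle which description is intended.

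**What to change.** 1. **Reconcile** the Section 3 sentence on groups 2-5, the Section 3 group list and the Section 6 total-dose statement before any regimen comparison. State which lamp each group uses.
2. **Allocate** subjects to groups 1-5 by a randomisation list. If the groups must run in sequence, say so and label the contrasts non-randomised. Treat comparisons with self-selected group 6 as descriptive.
3. **Prespecify one exploratory comparison** of groups 1-5: ANCOVA with regimen, baseline urine thymine dimer and baseline pigment. Report estimates with 95% confidence intervals beside the redness and pigment changes. Use one per-subject summary, such as the mean over days 1-4 after the last irradiation. Add a sensitivity analysis using all samples from the first irradiation to day 7 after the last; otherwise, early excretion would be dropped only in groups irradiated more than once. Do not read a non-significant contrast as equivalence.
4. **Amend Section 4** to say that the test is two-sided, if so, and what 1.3 nmol is the SD of. State that 0.80 applies only to the within-group before/after test. Give the detectable pairwise difference of about 2.0 to 1.7 nmol for 7 to 10 per group at an assumed SD of 1.3 nmol, unadjusted and with pooled variance, and its range for SD 1.0-1.6.

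**Cost.** A randomisation list, one model on data already collected and a few sentences; no extra subjects or samples. Groups 1-5 must recruit in parallel and subjects must accept any of them. The analysis grows slightly and the power statement becomes narrower. Intervals stay wide, about +/-1.2 to 1.4 nmol before covariate adjustment. How to trade dimers against redness and pigment remains for the sponsor to define.
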